The treatment strategy for patients with refractory VF/VT cardiac arrest should clearly include achievement of adequate coronary and cerebral perfusion by using mechanical CPR devices, optimizing hemodynamics, facilitating early transport, and providing ongoing treatment during transport. Compared with a strategy that provides these measures but requires ROSC before the patient can gain access to the CCL, the addition of early circulatory support by expediting ECMO initiation, can be used as the stabilization platform to facilitate PCI when clinically indicate. That approach is expected to significantly improve survival to hospital discharge and functionally favorable survival by 3-6 months post hospital discharge. However, emergent ECMO initiation at short notice with field activation carries significant human and infrastructural costs in addition to the technical, procedural, and management challenges that arise after the patient is hospitalized. Therefore, before major infrastructural investments can be made, both the contribution of **early ECMO facilitated resuscitation** to the management and survival of this population and the relative cost of such a strategy need to be assessed in a randomized clinical trial.

SUPPORTING SCIENCE – ANIMAL STUDIES:

IMPORTANCE OF CORONARY REVASCULARIZATION IN PORCINE MODEL OF REFRACTORY ISCHEMIC VF.

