2.3 RISK/BENEFIT ASSESSMENT

2.3.1 KNOWN POTENTIAL RISKS

Refractory cardiac arrest has a very grim prognosis. Survival from refractory VF/VT drops to <1% after 35 minutes of conventional CPR and resuscitation. Prolonged CPR is encountered universally in these patients and leads to multiple traumatic injuries that are unavoidable. Risks associated with chest compressions include traumatic injuries such as pneumothorax, hemopericardium, rib fractures, and solid organ injuries.

Standardized, mechanical CPR will be employed as the usual practice for all out-of-hospital cardiac arrest victims (randomized or not) with the included EMS agencies as an adjunct to manual cardiopulmonary resuscitation (CPR) when effective manual CPR is not possible (e.g., during patient transport, or extended CPR when fatigue may prohibit the delivery of effective/consistent compressions to the victim, or when insufficient personnel are available to provide effective CPR).

Risks associated with ECPR include mechanical failure, hemorrhagic, neurologic, renal, cardiovascular, pulmonary, metabolic, infections and ischemic complications. ECMO initiation will be attempted for all patients meeting criteria for the **Early ECMO Facilitated Resuscitation Protocol** and the **Standard ACLS Resuscitation Protocol** as currently and routinely practiced in the Minneapolis St. Paul area. Patient

presenting with ROSC may still be placed on ECMO when the clinical team deems it necessary for circulatory support when cardiogenic and or vasoplegic shock is present.

All patients with ROSC and pulses after VF/pVT OHCA enrolled in the ARREST trial will gain access to the CCL per standard of care. As such, those patients, in both groups will go to the CCL regardless of arm allocation.

Potential VA ECMO or other circulatory support device initiation in those patients is based on the interventional cardiologist's clinical judgment. In general, evidence of the following are considered common indications in all CCL patients:

- i) Profound cardiogenic shock with SBP < 90 mmHg or MAP < 60 mmHg despite inotropic support and an intra-aortic balloon pump,
- ii) Persistent hypoxia with arterial oxygen saturation < 90% despite maximum ventilatory support,
- iii) Florid pulmonary edema despite IV diuretics,
- iv) Recurrent episodes of VF or VT in the CCL,

In general <10% of the patient achieve ROSC before arrival to the CCL or in the ED.

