Standard ACLS Resuscitation. If the patient is randomized to this protocol, research personnel will notify the ED MD about the randomization. Patients who have not achieved ROSC continue on ACLS resuscitation after arrival in the ED. Patients receive continued ACLS treatment in the ED for at least 15 minutes following ED arrival or at least 60 minutes from 911 call. If ROSC is achieved in the ED, the CCL team is mobilized and the patient transferred to the CCL per standard University of Minnesota clinical practice. If the patient has ROSC in the ED, but continues to re-arrest, the CCL team will not be mobilized until the patient demonstrates ROSC (as determined by the treating clinician, consistent with current clinical practice). If the ED MDs deem the ACLS effort futile at any point after 15 minutes of CPR from ED arrival or 60 minutes after the 911 if known, they can declare death.

Patients presenting or achieving ROSC in both group arms.

All patients with ROSC and pulses after VF/pVT OHCA gain access to the CCL per standard of care at the University of Minnesota. As such, those patients, in both groups will go to the CCL **regardless of arm allocation.**

VA ECMO or other circulatory support device initiation in those patients is based on the interventional cardiologist's clinical judgment. In general, evidence of the following are common indications for VA ECMO initiation in all CCL patients:

- i) Profound cardiogenic shock with SBP < 90 mmHg or MAP < 60mmHg despite inotropic support and an intra-aortic balloon pump,
- ii) Persistent hypoxia with arterial oxygen saturation < 90% despite maximum ventilatory support,

- iii) Florid pulmonary edema despite IV diuretics,
- iv) Recurrent episodes of VF or VT in the CCL.

Post-resuscitation Critical Care Recommended Pathway

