The gross, billing charges per patient will be collected utilizing UB04 data for research purposes. The costs in each group will be averaged. Charges collected will include care in the emergency department (ED), CCL and inpatient care. The costs will be compared between groups and presented both as cost per patient and cost per patient per life saved.

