9.4.3 ANALYSIS OF THE SECONDARY ENDPOINT(S)

Secondary efficacy analyses will include survival to hospital discharge with mRS \leq 3, survival at 3 and 6 months, survival at 3 and 6 months with mRS \leq 3, functional status at discharge, 3 and 6 months (mRS

score and Cerebral Performance Category [CPC] score), cost per patient (based on billing charges), and cost per life saved (based on billing charges). These analyses will be performed both on an intention-to-treat and an as-treated basis. Categorical outcomes will be analyzed using Fisher's Exact Test or the logistic model. Quantitative outcomes (cost per patient and cost per life saved) will be analyzed using t-tests (with log transformation for skewed distributions as appropriate) and analysis of variance.

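### Cost per patient is reported as an average, but skewed charges may be tested on the log scale, which compares geometric means rather than those averages

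*Combined protocol and SAP*

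**What the plan says.** Section 8.1 sets out the data and the summary. "The gross, billing charges per patient will be collected utilizing UB04 data for research purposes", covering ED, catheterization laboratory and inpatient care. Then: "The costs in each group will be averaged". And: "The costs will be compared between groups and presented both as cost per patient and cost per patient per life saved".

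Section 9.4.3 gives the test. Cost per patient and cost per life saved "will be analyzed using t-tests (with log transformation for skewed distributions as appropriate) and analysis of variance". For all secondary efficacy endpoints it adds: "These analyses will be performed both on an intention-to-treat and an as-treated basis".

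The plan gives no rule for when logs are appropriate, no back-transformation, and no interval for a difference or ratio of average charges. It states no mean, standard deviation or distribution of charges.

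Cost is one of the reasons given for the trial. Section 2.2 says that "the relative cost of such a strategy need to be assessed in a randomized clinical trial".

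**The concern.** The summary and the test can refer to different quantities. The averages in section 8.1 are arithmetic means. A t-test on logs compares mean log charges, that is, geometric means. The two contrasts agree only if the arms have similarly shaped charge distributions.

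Similar shapes are unlikely here. In the standard arm, section 6.1.1 lets death be declared in the ED ("If the ED MDs deem the ACLS effort futile at any point after 15 minutes of CPR from ED arrival"), and only patients with ROSC go on to the catheterization laboratory. Section 2.3.1 puts that share low: "In general <10% of the patient achieve ROSC before arrival to the CCL or in the ED". In the early-ECMO arm, section 6.1.1 sends patients to the catheterization laboratory with or without ROSC, and expects those placed on ECMO to need about 3 to 5 days of support or longer. Each arm is then a mixture of low-charge early deaths and high-charge admissions, in very different proportions. Such data would prompt a log transformation, and they are also the data in which geometric and arithmetic contrasts separate.

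At stake is whether the p-value printed beside the average charges says anything about those averages. A budget depends on the average charge, not on the geometric mean. The scale is also left open until the data are seen, although the two permitted analyses can disagree.

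**Working it through.** The plan states no cost figure, so there is none to reproduce. The checks below show how far the two contrasts can differ.

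**Inputs**
- Standard-arm share admitted beyond the ED, aC: 12%, the planning survival rate in section 9.2, since a survivor must have been admitted. Section 2.3.1 suggests below 10%. Range tried: 10% to 20%.
- ECMO-arm share passing beyond early termination, aE: 55/62 = 0.887, from the 62 protocol patients and the 55 used as the balloon-pump denominator in section 6.1.1. Using this as an admission share is an assumption; 60% is also tried.
- Charge of an admitted patient relative to an early death, R: not in the documents. Assumed 5 to 50.

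**Check 1: two-point mixture**
- Ratio of arithmetic means, AMR = [(1 − aE) + aE·R] / [(1 − aC) + aC·R]
- Ratio of geometric means, GMR = R^(aE − aC)
- Distortion = GMR / AMR

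Example, R = 10: AMR = (0.113 + 8.871)/(0.88 + 1.20) = 4.32; GMR = 10^0.767 = 5.85; distortion 1.35.

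| R | AMR (12% vs 55/62) | GMR | GMR/AMR | GMR/AMR (12% vs 60%) |
|---|---|---|---|---|
| 5 | 3.07 | 3.44 | 1.12 | 0.94 |
| 10 | 4.32 | 5.85 | 1.35 | 0.98 |
| 20 | 5.44 | 9.95 | 1.83 | 1.11 |
| 30 | 5.97 | 13.59 | 2.28 | 1.25 |
| 50 | 6.46 | 20.10 | 3.11 | 1.48 |

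With aE at 55/62, the factor runs from 1.09 to 2.88 if 10% of the standard arm is admitted, and from 1.20 to 3.57 if 20% is. It equals 2 at R of about 27, 24 and 18 for aC of 10%, 12% and 20%.

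**Check 2: unequal early-death charges**

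Let d be the share of early deaths, m their mean charge and M the mean charge of an admitted patient. A common coefficient of variation within groups cancels from both ratios. All dollar figures are assumed.
- dC = 80% at $30k, dE = 20% at $60k, M = $300k: AMR = (12 + 240)/(24 + 60) = 3.0; GMR = 4.6; factor 1.5.
- dC = 88% at $20k, dE = 15% at $60k, M = $400k: AMR = (9 + 340)/(17.6 + 48) = 5.3; GMR = 10.5; factor 2.0.
- dC = 93% at $15k, dE = 10% at $60k, M = $500k: AMR = (6 + 450)/(13.95 + 35) = 9.3; GMR = 21.1; factor 2.3. This case leaves at most 7% of the standard arm alive, below the 12% planning rate.

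**Check 3: log-normal charges with log-SDs sC and sE**

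GMR/AMR = exp[(sC² − sE²)/2]. Equal log-SDs give 1.00. sC = 1.2 with sE = 0.5 gives exp(0.595) = 1.81; the reverse gives 0.55. A factor of 2 needs sC² − sE² = 2·ln 2 = 1.39.

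**Check 4: rejection rates (simulation)**
- Equal arithmetic means, log-SDs 1.2 and 0.5, 75 per arm: the log t-test rejects in 97% of trials and the untransformed Welch test in 9%. With equal log-SDs of 1, both reject in about 5%.
- Five settings within or near the Check 2 assumptions, at 52 versus 29 patients (the average arm sizes under the alternative in section 9.1): Welch rejects in 96% to 99.9% of trials and the log test in about 100%, in the same direction.

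**The case against.** The strongest reply is that little would be misreported. Section 8.1 presents arithmetic averages, and those stand whatever test is used. Section 9.4.3 names tests only; it plans neither a back-transformed ratio nor an interval. Logs apply only where appropriate, so an untransformed t-test, which does compare averages, remains within the plan. Cost is one of several secondary endpoints in a Phase II trial, and no stopping or success rule uses it. All of this is correct.

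A reader might infer more than the documents support in two ways.
- That the trial will overstate the relative cost of early ECMO about two-fold. This presupposes a geometric-mean ratio that the plan does not say it will report, and a charge distribution that the documents do not give. The factor falls below 1 in some settings, so an upward direction is likely but not certain.
- That the log test would nearly always declare a false difference. The 97% figure needs equal average charges. Under the charges assumed in Check 2 the averages differ 3.0- to 9.3-fold, and both tests almost always reject.

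What survives is narrower. If logs are used, the test does not refer to the reported averages, and the plan has no stated way to put uncertainty around the contrast of averages.

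**Conclusion.** The mismatch is real and rests on the text alone: averages in section 8.1, and a log-scale t-test as the only stated remedy for skewness in section 9.4.3. Its size cannot be fixed from the documents. At admission shares of 12% and 55/62, and assumed charge ratios of 5 to 50, the geometric-mean ratio is about 1.1 to 3.1 times the ratio of averages. With 60% of the ECMO arm admitted it is 0.94 to 1.48 times. The likely consequence is a p-value that does not match the figures beside it and no usable interval, rather than a wrong average or a reversed conclusion.

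A related gap lies in the same sentence. Cost per life saved is a ratio formed at group level, with no patient-level values, so a t-test does not apply to it directly.

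This is a point to consider: worth correcting because it is cheap, not because any trial decision depends on it.

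**What to change.** In section 9.4.3:

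1. Make the difference in arithmetic mean charges per randomised patient, in the intention-to-treat population, the main cost-per-patient analysis. Give a 95% bootstrap interval resampled within arm, or an untransformed Welch interval.
2. Keep any log-scale analysis as supportive only, labelled as a comparison of geometric means.
3. If a ratio of means is also shown, warn that its percentile bootstrap interval under-covers when few standard-arm patients are admitted. In simulations at 52 versus 29, where the standard arm holds only about 2 to 6 admitted patients, coverage was about 79% to 91% for the ratio, against about 92% to 94% for the difference.
4. Report cost per life saved as a group-level ratio with a bootstrap interval, and drop the t-test for it. With about 29.2 × 0.12 = 3.5 expected standard-arm survivors under the planning alternative, this interval may be unstable. The plan should say what is done when a resample contains no survivors.

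The cost is a few sentences in the plan and a little more analysis work, with no change to data collection, conduct or sample size. The downside is wider intervals than on the log scale, which reflect the real uncertainty in average charges.

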9.4.4 SAFETY ANALYSES

The incidence of AEs will be recorded for all patients in the safety population and presented by treatment arm to the DSMB for review during the study, as well as summarized and compared across treatment arms in the final report of study results. AEs attributable to advanced reperfusion strategies will be reported separately. The statistical significance of differences in safety signal incidence between the 2 treatment groups will be reported. Emphasis will be placed on the presentation of primary study results, with statistical tests provided for guidance on the precision of estimates as indicated. The DSMB must weigh risks against benefits. Thus, interim presentations to the DSMB will include between-group comparisons of the relation of severe adverse events (including deaths) to favorable outcomes. Similar considerations apply to publication of study results when the trial is completed. The specific adverse events listed that potentially reflect the safety of the Early ECMO Facilitated Resuscitation may or may not affect survival to hospital discharge or longer term functional outcome.

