8.3 ADVERSE EVENTS AND SERIOUS ADVERSE EVENTS

8.3.2 DEFINITION OF SERIOUS ADVERSE EVENTS (SAE)

Any adverse event that results in any of the following outcomes: death, a life-threatening adverse event, inpatient hospitalization or prolongation of existing hospitalization, a persistent or significant disability/incapacity, or a congenital anomaly/birth defect.

- *Hospitalization* shall include any initial admission (even if less than 24 hours) to a healthcare facility as a result of a precipitating clinical adverse event. Hospitalization or prolongation of hospitalization in the absence of a precipitating, clinical adverse event (e.g., for a preexisting condition not associated with a new adverse event or with a worsening of the preexisting condition; admission for a protocol-specified procedure) is not, in itself, a serious adverse event.

Unexpected adverse event. Any adverse event, the frequency, specificity or severity of which is not consistent with the risk information described in the clinical study protocol(s) or elsewhere in the current IDE application, as amended.

Unanticipated adverse device event. Any serious adverse event on health or safety or any life-threatening problem or death caused by, or associated with, a device, if that event, problem, or death was not previously identified in nature, severity, or degree of incidence in the investigational plan or IDE application (including a supplementary plan or application), or any other unanticipated serious problem associated with a device that relates to the rights, safety, or welfare of subjects.

Disability. A substantial disruption of a person's ability to conduct normal life functions.

Life-threatening adverse event. Any adverse event that places the subject, in the view of the investigator-sponsor, at immediate risk of death from the event as it occurred (i.e., does not include an adverse event that, had it actually occurred in a more severe form, might have caused death).

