8.3.3.3 EXPECTEDNESS

Adverse Events Common to Both Treatment Arms due to CPR and prolonged ischemic times

1. Infection/sepsis (Infection: any infection requiring intervention by the treating clinicians; Sepsis: systemic inflammatory response syndrome in response to an infectious process (confirmed by the treating clinicians))

2. Acute kidney injury (AKI) (Confirmed by the treating clinicians). (Increase in serum creatinine ≥ 0.3 mg/dl (≥ 26.5 $\mu\text{mol/l}$) within 48 hours, or increase in serum creatinine ≥ 1.5 times baseline, or Urine volume < 0.5 ml/kg/h for 6 hours, or Urine volume < 0.5 ml/kg/h for 6 hours)
3. Liver failure/injury (Rapid development of hepatocellular dysfunction in a patient without known prior liver disease (confirmed by the treating clinicians)
4. Cardiogenic shock (Intervention required to maintain adequate hemodynamics (confirmed by the treating clinicians)
5. Multiple organ dysfunction syndrome (MODS) Two or more organs in which homeostasis cannot be maintained without intervention (confirmed by the treating clinicians)
6. Seizure activity (Documented by EEG or clinical assessment and confirmed by the treating clinicians)
7. Brain death (**Brain Death** (*The Canadian Neurocritical Care Guideline*) defined brain death as the irreversible loss of the capacity for consciousness combined with the irreversible loss of all brainstem functions, including the capacity to breathe. Brain death is equivalent to death of the individual, even though the heart continues to beat and spinal cord functions may persist (Citation in Data Definitions) **Neurological determination of death (NDD)** is the process and procedure for determining brain death. The Canadian medical standard for NDD is reported in and is described for children. **Ancillary Tests:** The demonstration of the absence of intracerebral blood flow is considered the standard as an ancillary test for brain death. Currently validated imaging techniques are cerebral angiography (1) and radionuclide angiography (2. **Apnea Test on ECMO:** The patient should be placed on continuous positive airway pressure (CPAP) while the sweep gas flow rate is set to a maximum of 1.0 liter/minute. If the PaCO₂ does not rise above 60 mmHg or change by 20 mmHg, the sweep flow can be incrementally lowered to as low as 0.1 liter/minute while still maintaining adequate oxygenation in most circumstances.)
8. Recurrent cardiac arrest
9. Survival to hospital discharge with mRS >3

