8.3.5 ADVERSE EVENT REPORTING

This very critically ill study population is recognized and expected to experience initial and repeated life threatening events throughout resuscitation and hospitalization. Accordingly, following consultation with the Food and Drug Administration, investigators will not track or report adverse events, expected to be nearly continuous in all patients.

Serious adverse events will be tracked and reported as described below. Investigators will further track the frequency of serious adverse events, compare the study frequency with patients treated similarly previous to and outside the study, and report any significant increased frequency based on investigator clinical judgment and experience.

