9.4.8 TABULATION OF INDIVIDUAL PARTICIPANT DATA

Patients in this trial will have complex clinical courses prior to hospital discharge. They will experience a wide variety of adverse events, many of them serious, some of them known complications of ECMO treatment. The Statistical and Data Coordinating Center will maintain detailed histories, by hospital course day, of adverse events and treatments. Tables comprised of such detailed histories will be available for examination by members of the DSMB. DSMB summary tables will classify the nature and frequency of adverse events essentially by collapsing such histories across treatment groups and other strata of interest.

All data in SDCC files, reports, or tables will be de-identified.

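### Non-fatal in-hospital SAEs will be significance-tested by arm with no allowance for time at risk, although most standard-arm patients probably die in the ED

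*Combined protocol and SAP*

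**What the plan says.** Section 9.4.4 sets the denominator and the comparison: "The incidence of AEs will be recorded for all patients in the safety population and presented by treatment arm to the DSMB", followed by "The statistical significance of differences in safety signal incidence between the 2 treatment groups will be reported". It then describes the tests as "with statistical tests provided for guidance on the precision of estimates as indicated". The safety population is not defined in 9.3 or elsewhere.

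Although 9.4.4 speaks of AEs, section 8.3.5 says that "investigators will not track or report adverse events, expected to be nearly continuous in all patients", so in practice the comparison concerns SAEs. Section 8.3.2 defines an SAE as "Any adverse event that results in any of the following outcomes: death, a life-threatening adverse event", among other outcomes, so death itself counts.

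Sections 9.4.6 and 10.1.4 have the DSMB compare adverse event rates every six months, again with no denominator. Section 9.4.8 says that the coordinating center "will maintain detailed histories, by hospital course day, of adverse events and treatments", but the DSMB summary tables are to collapse those histories. No section mentions time at risk or death as a competing event.

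**The concern.** The two strategies differ in how many patients live long enough to have an in-hospital complication. In the standard arm, a patient without ROSC is not offered ECMO (2.3.2) and may be declared dead in the ED (6.1.1). Such a patient cannot later develop sepsis, critical illness myopathy or late seizures. Early-ECMO patients go to the CCL whether or not they have ROSC, and 6.1.1 expects those placed on ECMO to need 3-5 days or longer of support.

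A by-arm test of such events therefore largely measures who reached admission. The clearest example is in 8.3.3.3, which lists discharge alive with mRS >3 as an adverse event. Only survivors can have it, so its incidence can rise simply because fewer patients die.

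Safety is a stated objective (section 3), and the results are meant to inform a later multicenter trial (9.4.1). A small p-value that reflects survival could be read as toxicity, or could blur a true difference in daily risk.

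**Working it through.** **1. The plan's own figures.** The documents give no SAE incidence to reproduce. The design figures in 9.1 supply the group sizes. A simulation of 10,000 trials per scenario used Beta(1,1) priors, looks every 30 up to 150, threshold 0.986, and the next block's ECMO probability equal to the posterior, kept within 0.25-0.75. It gave power 0.901-0.902 (stated 0.905), type I error 0.049 (stated 0.048) and average N 82.8-83.0 under the alternative (stated 81.6). The checks below use 75/75 (balanced full trial), 52/29 (close to the stated alternative averages of 52.5 and 29.2) and 15/15 (first look).

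**2. Standard-arm share admitted.** Survival in this arm requires ROSC, so share admitted ≈ survival / survival after ROSC.
- Survival: 11/162 = 6.8% (2.3.2, regional standard care) or 12% (9.2, design).
- Survival after ROSC: 222/411 = 54% or 22/33 = 67% (both 2.3.2).
- Lowest: 0.068/0.667 = 10%. Highest: 0.12/0.54 = 22%. From 0.12/0.667: 18%, used as the central value.

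So about 78-90% die in the ED. The low end agrees with 2.3.1: "In general <10% of the patient achieve ROSC before arrival to the CCL or in the ED".

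**3. Early-ECMO share admitted.** This is assumed to be 60-89%. The upper end reads 55 of 62 patients in 6.1.1 (ECMO Exposure) as those reaching inpatient care. The lower end allows for deaths declared in the CCL under 6.1.1. The central value is 75%.

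**4. Crude incidence at equal daily risk.** Incidence = share admitted × (1 − exp(−h·T)), with daily hazard h and stay T assumed.
- Central case, h = 0.05 and T = 10 days: 0.75 × 0.393 = 29.5% vs 0.18 × 0.393 = 7.1%, ratio 4.2.
- With equal h and T in both arms, the ratio is just the ratio of admission shares: 0.60/0.22 = 2.7 to 0.887/0.10 = 8.9.
- Unequal stays, central shares: 2.6 (ECMO 10 days, standard 20) to 6.7 (20 vs 10).

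**5. Chance of Fisher p<0.05 with no difference in daily risk** (T = 10 days; the range covers h = 0.02-0.10 and the admission shares above):

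| Group sizes | Central case, h = 0.05 | Range |
|---|---|---|
| 75/75 | 93% | 25-100% |
| 52/29 | 65% | 12-100% |
| 15/15 | 21% | 1-78% |

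**6. Where the excess shrinks or disappears.**
- Events that can also occur before admission, with common background b: incidence = 1 − (1 − b)(1 − crude incidence). For b = 10%: 36.6% vs 16.4%, ratio 2.2. For b = 30%: 50.7% vs 35.0%, ratio 1.45. For b = 50%: 64.8% vs 53.5%, ratio 1.2.
- Any SAE including death, at design survival, with a share q of survivors having another SAE: (0.63 + 0.37q)/(0.88 + 0.12q). This is 0.72 at q = 0 and rises only to 1.0 at q = 1.

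**7. Patient-day comparison.** With the central shares, h = 0.05 and equal true daily risk, 4,000 simulated trials gave a median rate ratio of about 1.01. A conditional Poisson test rejected in about 4% of trials at both 75/75 and 52/29.

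**The case against.** Several objections have force.

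- **A reader might infer that ED deaths are never at risk of an SAE, or that ECMO will look several times more harmful overall.** The documents do not support this. Death is an SAE under 8.3.2, so an ED death counts against the standard arm. The list in 8.3.3.3 headed "Adverse Events Common to Both Treatment Arms due to CPR and prolonged ischemic times" includes rib and sternal fractures and pneumothorax, which can precede an ED death.
- **That the comparison is a crude proportion is inferred.** Section 9.4.4 says incidence, while 9.4.6 and 10.1.4 say rate. The firm statement is that the denominator is unspecified. The collapsing of histories in 9.4.8 makes the crude reading the likely one.
- **There are safeguards.** Tests are for guidance, events attributable to reperfusion strategies are reported separately, and the DSMB sees severe events, including deaths, against favorable outcomes. The only numerical stopping threshold concerns survival. These points lower the stakes but do not correct the contrast for sepsis, kidney injury or seizures.
- **Total event burden by assigned strategy is a legitimate intention-to-treat question.** Excess bleeding or limb ischemia caused by ECMO is real harm. This stands, and is why the by-arm percentages should remain.
- **The usual remedies have limits.** With complete in-hospital follow-up, cumulative incidence with death as a competing event ends at the same value as the crude proportion. A composite of death or any SAE adds nothing, because death is already an SAE. Patient-day rates compare most of the ECMO arm with the few standard-arm patients who obtained ROSC, so they condition on a post-randomization outcome.
- **The inputs are soft.** The ROSC figure below 10% does not fit the 12% design survival, since survival in that arm needs ROSC; the two should be reconciled. The 54% describes patients with ROSC within three shocks, whom 2.3.2 calls healthier. If survival after ROSC were 40% (assumed), 0.12/0.40 = 30% would be admitted and the ratio would be 2.0-3.0. Most standard-arm patients would still die in the ED.

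**Conclusion.** The point holds for non-fatal SAEs that arise after admission. For these, 9.4.4 plans a by-arm significance statement with no allowance for time at risk, in a trial where about 78-90% of one arm probably dies in the ED. Equal daily risk would show as about a 3- to 9-fold crude excess with ECMO. The excess is about 1.2-2.2 for events with a 10-50% pre-admission background, and there is none for any SAE including death.

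The gap in the text is certain. The size rests on derived or assumed admission shares, a constant and equal daily hazard, and equal stays. The hazard cancels from the ratio when stays are equal, but it drives the chance of a spurious p-value. The documents do not support a conclusion that the whole safety comparison is biased against ECMO. This is a worthwhile, inexpensive improvement to the analysis and does not affect the primary result.

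**What to change.** In 9.3 and 9.4.4:

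- State that the safety population is all eligible randomized patients, by assigned arm.
- Keep by-arm percentages for each SAE type as description, without p-values. Show deaths in the ED or CCL before admission on their own row.
- For non-fatal in-hospital SAEs, add events per patient-day alive in hospital by arm, from the 9.4.8 histories. Label this a supplement, because it conditions on surviving to admission.
- For each key non-fatal SAE type, show its cumulative incidence beside the death curve, or a composite of death or that specific SAE. Do not claim that competing-risk incidence removes the imbalance.
- Report events caused by ECMO in full, as real harm.

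The cost is a little more programming for the DSMB and final tables. On the description in 9.4.8, no new data are needed. The price in interpretation is that the patient-day comparison is not a purely randomized contrast and must be read beside the by-arm table.
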